3.3.6.2 Criteria to Resume Pembrolizumab Treatment

Subjects may resume treatment with study drug when the drug-related AE(s) resolve to Grade ≤ 1 or baseline value, with the following exceptions:

- Subjects may resume treatment in the presence of Grade 2 fatigue.
- Subjects who have not experienced a Grade 3 drug-related skin AE may resume treatment in the presence of Grade 2 skin toxicity.
- Subjects with baseline Grade 1 AST/ALT or total bilirubin who require dose delays for reasons other than a 2-grade shift in AST/ALT or total bilirubin may resume treatment in the presence of Grade 2 AST/ALT OR total bilirubin.
- Subjects with combined Grade 2 AST/ALT AND total bilirubin values meeting discontinuation parameters should have treatment permanently discontinued.
- Drug-related pulmonary toxicity, diarrhea, or colitis, must have resolved to baseline before treatment is resumed. Subjects with persistent Grade 1 pneumonitis after completion of a steroid taper over at least 1 month may be eligible for retreatment.
- Drug-related endocrinopathies adequately controlled with only physiologic hormone replacement may resume treatment.

If the criteria to resume treatment are met, the subject should restart treatment at the next scheduled time point per protocol. However, if the treatment is delayed past the next scheduled time point per protocol, the next scheduled time point will be delayed until dosing resumes.

If treatment is delayed or interrupted for > 6 weeks, the subject must be permanently discontinued from study therapy unless there is evidence (stable disease or disease regression) of clinical benefit.

3.4 ON STUDY PROTOCOL EVALUATION (APPENDIX 3: STUDY CALENDAR)

3.4.1 Baseline Assessments

Note: Baseline assessments do not need to be repeated if performed during screening in the designated time frame.

Any Time Prior to Initiation of Treatment:

- a. HLA class I and class II analysis of PBMC.
- b. Tumor biopsy if fresh sample from previous biopsy is not available. Note: Samples collected on 06C0014 or any other NCI protocol in which the patient is co-enrolled can be used.

Within 10 Days Prior to Commencing DAC-THU/Pembrolizumab Therapy:

- a. Physical examination including assessment of vital signs and ECOG status.
- b. Chemistries
 - i. Acute Care Panel Sodium (Na), Potassium (K), Chloride (Cl), Total CO2 (bicarbonate), Creatinine, Glucose, Urea nitrogen (BUN),
 - ii. Mineral Panel Albumin, Calcium total, Magnesium total (Mg), Phosphorus
 - iii. Hepatic Panel Alkaline Phosphatase, ALT/GPT, AST/GOT, Total Bilirubin, Direct Bilirubin
 - iv. LD, Total Protein, Total CK, Uric Acid
- c. Fetal hemoglobin
- d. CBC, differential, platelet count, PT, PTT
- e. T, B, NK cell subsets
- f. Urinalysis and culture if indicated
- g. Pulmonary Function Test
- h. Arterial Blood Gas on room air (to be drawn if pulse oximetry <90% on room air).
- i. Research Labs (refer to Appendix 4 for details).

Within 48 Hours Prior to Initiation of DAC-THU/Pembrolizumab Therapy:

a. Women of child-bearing potential will have a urine or serum βhCG pregnancy test.

3.4.2 Treatment Evaluation

Twice Weekly During First Course of Therapy, and Weekly Thereafter Unless Clinically Indicated:

- a. CBC with differential
- b. Sodium (Na), Potassium (K), Chloride (Cl), Total CO2 (bicarbonate), Creatinine, Glucose, Urea nitrogen (BUN), Albumin, Calcium total, Magnesium total (Mg), Phosphorus, Alkaline Phosphatase, ALT/GPT, AST/GOT, Total Bilirubin, Direct Bilirubin, LD, Total Protein, Total CK, Uric Acid
- c. PT/PTT

Note: The patient may have lab work obtained through his or her local physician.

Every Three Weeks During Therapy:

a. T, B, NK cell subsets

Performed After Each Course:

- a. Physical examination including assessment of vital signs and ECOG status.
- b. Sodium (Na), Potassium (K), Chloride (Cl), Total CO2 (bicarbonate), Creatinine, Glucose, Urea nitrogen (BUN), Albumin, Calcium total, Magnesium total (Mg), Phosphorus, Alkaline Phosphatase, ALT/GPT, AST/GOT, Total Bilirubin, Direct Bilirubin, LD, Total Protein, Total CK, Uric Acid
- c. CBC, differential, platelet count, PT, PTT
- d. Thyroid Function Tests
- e. T, B, NK cell subsets
- f. Urinalysis and culture if indicated
- g. Biopsy of index lesion (only on first treatment evaluation).

3.4.3 Research Evaluations (Refer to Appendix 4, Unless Otherwise Indicated Below)

- Pharmacokinetic (PK) Studies
- Research Labs
- Radiological Assessments (refer to Appendix 3)
- Tumor Biopsies (see Appendix 3)

3.4.4 Follow-Up Evaluations

Patients who are removed from treatment due to disease progression or unacceptable, dose-limiting toxicities or who voluntarily withdraw from treatment will be monitored weekly until treatment related toxicities have resolved to baseline at which time they will be removed from study.

Toxicity Evaluation:

 Laboratory evaluation: CBC, Chemistries (Sodium, potassium, chloride, bicarbonate, creatinine, glucose, BUN, albumin, total calcium, ionized calcium, magnesium, phosphorus, alkaline phosphatase, ALT/SGPT, AST/SGOT, total bilirubin, direct bilirubin, lactate dehydrogenase, total protein, creatine kinase, uric acid), PT/PTT

3.5 COSTS AND COMPENSATION

3.5.1 Costs

NIH does not bill health insurance companies or participants for any research or related clinical care that participants receive at the NIH Clinical Center. If some tests and procedures are performed outside the NIH Clinical Center, participants may have to pay for these costs if they are not covered by their insurance company. Medicines that are not part of the study treatment will not be provided or paid for by the NIH Clinical Center.

3.5.2 Compensation

Participants will not be compensated on this study.

3.5.3 Reimbursement

The NCI will cover the costs of some expenses associated with protocol participation. Some of these costs may be paid directly by the NIH and some may be reimbursed to the participant/guardian as appropriate. The amount and form of these payments are determined by the NCI Travel and Lodging Reimbursement Policy.

3.6 CRITERIA FOR REMOVAL FROM PROTOCOL THERAPY AND OFF STUDY CRITERIA

Prior to removal from protocol, effort must be made to have all subjects complete a safety visit approximately 30 days after the last dose of study therapy.

3.6.1 Criteria for Removal from Protocol Therapy

- Patient refusal of further treatments
- It is deemed in the best interest of the patient
- A patient who develops a concurrent serious medical condition that might preclude or contraindicate administration of DAC-THU/pembrolizumab therapy will be removed from treatment
- A patient who becomes pregnant will be immediately taken off therapy
- Progressive disease
- Failure to meet criteria for additional treatment as defined in Sections 3.3.2 and 3.3.6
- Delay of treatment for three weeks

Note: Patients will be followed until toxicities related to experimental therapy resolve to baseline.

3.6.2 Off-Study Criteria

- Voluntary withdrawal for any reason, or noncompliance with protocol requirements
- Completion of the follow up period (see Section **3.4.4**)
- Progressive disease unless the patient is being followed for a serious adverse event related to the research. The event must resolve to baseline prior to removing from the study

- If the investigator determines that it is in the best interest of the patient to discontinue follow up
- Lost to follow up
- Death
- PI decision to close the study

3.6.3 Lost to Follow-Up

A participant will be considered lost to follow-up if he or she fails to return for 3 scheduled visits and is unable to be contacted by the study site staff.

The following actions must be taken if a participant fails to return to the clinic for a required study visit:

- The site will attempt to contact the participant and reschedule the missed visit within 5 business days and counsel the participant on the importance of maintaining the assigned visit schedule and ascertain if the participant wishes to and/or should continue in the study.
- Before a participant is deemed lost to follow-up, the investigator or designee will make every effort to regain contact with the participant (where possible, 3 telephone calls/video calls and, if necessary, an IRB approved certified letter to the participant's last known mailing address or local equivalent methods). These contact attempts should be documented in the participant's medical record or study file.
- Should the participant continue to be unreachable, he or she will be considered to have withdrawn from the study with a primary reason of lost to follow-up.

4 CONCOMITANT MEDICATIONS/MEASURES

4.1 HEMATOLOGIC AND BLOOD PRODUCT SUPPORT

Blood product support should be provided to maintain platelets > 20,000 cells/mcl, Hgb > 8.0 gm/dl and as clinically indicated. Growth factor support is not permitted with exception of administration of filgrastim. Filgrastim will not be administered prophylactically, but may be administered if a patient experiences neutropenic sepsis, or if clinically indicated.

4.2 ANTIDIARRHEALS

Antidiarrheal agents will be prescribed using standard clinical practice guidelines at the preference of the investigator.

4.3 ELECTROLYTE REPLACEMENT

Electrolyte replacement will be provided to maintain serum levels within normal limits.

4.4 **PROTON PUMP INHIBITORS**

Given the uncertainties regarding effects of proton pump inhibitors on absorption of DAC-THU, proton pump inhibitors will not be used except on days when DAC-THU is not administered.

5 CORRELATIVE STUDIES

5.1 BIOSPECIMEN COLLECTION AND PROCESSING FOR RESEARCH

5.1.1 Pharmacokinetic (PK) Sampling

Detailed plasma pharmacokinetic (PK) sampling of DAC and THU will be collected as outlined in **Appendix 4**. PK analysis will be performed at the NCI, Genitourinary Malignancies Branch (GMB). Samples will be stored in the Thoracic Epigenetics Lab (TEL) and batched and later transferred to the [name] Lab on dry ice for analysis.

5.1.2 Studies on Tumor Tissue and Peripheral Blood

Portions of biopsy materials will be sent for frozen section or permanent section confirmation of malignancy and percent viable tumor cells. Tissue will be processed for focused gene, endogenous retroviral (ERV) and microRNA expressions, and DNA methylation signatures using quantitative RT-PCR, nanostring, pyrosequencing and digital droplet PCR techniques. Blood from EDTA and red top tubes (see **Appendix 4**) will be used to isolate plasma circulating tumor DNA and serum for focused methylation analysis and immune response to treatment. Remaining tissue samples will be snap frozen in liquid nitrogen for subsequent isolation of RNA and DNA for qRT-PCR and nanostring experiments. If sufficient tissue is available, another portion will be imbedded in paraffin for subsequent immunostaining experiments, focusing on expression of genes focusing on those proteins encoded by genes that have been identified to be clearly activated by epigenetic therapy. If sufficient materials are present, additional more comprehensive analyses including multiplex IHC analysis of tumor microenvironment may be performed with the focus of materials from patients treated at the MTD. All of the analyses, which are predicated on acquisition of sufficient materials, will be performed in the Thoracic Epigenetics Lab under direction of the PI or submitted to sequencing cores at the NCI.

5.1.3 Immune Subset Analyses

Peripheral blood mononuclear cells (PBMC) will be assessed using multiparameter flow cytometry for immune subsets including but not necessarily limited to Tregs, MDSC, effector and exhausted CD4+ or CD8+ T-cells, and CD14+ monocytes. Assessment will include functional markers, i.e. PD-1, PD-L1, Tim-3, CTLA-4, HLA-DR and/or CD40. Samples will be drawn (as indicated in **Appendix 4**) and picked up by the [name] Lab (see Section **5.2.4**) for analysis. The [name] Lab will prepare the samples for staining, stain and run the samples by multiparametric flow cytometry (MACSQuant, Miltenyi Biotec, Bergisch Gladbach, DE), and analyze the data using FlowJo (FlowJo LLC, Ashland, OR) software.

5.1.4 Circulating Tumor Cells

Peripheral blood will be collected to correlate changes in circulating tumor cells with clinical response. CTCs will be assessed using ferrofluidic enrichment and multi-parameter flow cytometric detection. Samples will be drawn (as indicated in **Appendix 4**) and picked up by the [name] Lab (Section **5.2.4**) for analysis. The [name] Lab will process the samples, stain and run one tube immediately. The other tube will be processed, 2D barcoded and viably stored for potential future analysis. The samples will be analyzed by multiparametric flow cytometry (MACSQuant, Miltenyi Biotec, Bergisch Gladbach, DE) and FlowJo (FloJo LLC, Ashland, OR) software.

5.2 SAMPLE STORAGE, TRACKING AND DISPOSITION

Samples will be ordered and tracked through Clinical Trial Data Management System. Should a CRIS screen not be available, the CRIS downtime procedures will be followed. Samples will not be sent outside NIH without appropriate approvals and/or agreements, if required.

5.2.1.2 Sample Data Collection

All samples sent to the Blood Processing Core (BPC) will be barcoded, with data entered and stored in the Labmatrix utilized by the BPC. This is a secure program, with access to Labmatrix limited to defined [name] lab personnel, who are issued individual user accounts. Installation of Labmatrix is limited to computers specified by [name]. These computers all have a password restricted login screen.

Labmatrix creates a unique barcode ID for every sample and sample box, which cannot be traced back to patients without Labmatrix access. The data recorded for each sample includes the patient ID, name, trial name/protocol number, time drawn, cycle time point, dose, material type, as well as box and freezer location. Patient demographics associated with the clinical center patient number are provided in the system. For each sample, there are notes associated with the processing method (delay in sample processing, storage conditions on the ward, etc.).

5.2.1.3 Sample Storage and Destruction

Barcoded samples are stored in barcoded boxes in a locked freezer at either -20 or -80°C according to stability requirements. These freezers are located onsite in the BPC and offsite at NCI Frederick Central Repository Services in Frederick, MD. Visitors to the laboratory are required to be accompanied by laboratory staff at all times.

Access to stored clinical samples is restricted. Samples will be stored until requested by a researcher named on the protocol. All requests are monitored and tracked in Labmatrix. All researchers are required to sign a form stating that the samples are only to be used for research purposes associated with this trial (as per the IRB approved protocol) and that any unused samples must be returned to the BPC. It is the responsibility of the NCI Principal Investigator to ensure that the samples requested are being used in a manner consistent with IRB approval.

Following completion of this study, samples will remain in storage as detailed above. Access to these samples will only be granted following IRB approval of an additional protocol, granting the rights to use the material.

If, at any time, a patient withdraws from the study and does not wish for their existing samples to be utilized, the individual must provide a written request. Following receipt of this request, the samples will be destroyed (or returned to the patient, if so requested). The PI will record any loss

or unanticipated destruction of samples as a deviation. Reporting will be per the requirements of Section 7.2.

Sample bar-codes are linked to patient demographics and limited clinical information. This information will only be provided to investigators listed on this protocol, via registered use of Labmatrix. It is critical that the sample remains linked to patient information such as race, age, dates of diagnosis and death, and histological information about the tumor, in order to correlate genotype with these variables.

5.2.2 Procedures for Storage of Tissue Specimens in the Laboratory of Pathology

Tissues designated for clinical diagnostics are transported to the Laboratory of Pathology (LP) where they are examined grossly and relevant portions fixed, embedded in paraffin and sectioned and stained for diagnostic interpretation. Unutilized excess tissue that is not embedded in paraffin is stored in formalin for up to three months, in accordance with College of American Pathologists/Joint Commission on Accreditation of Healthcare Organizations (CAP/JCAHO) guidelines, and then discarded. Following completion of the diagnostic workup, the slides and tissue blocks are stored indefinitely in the LP's clinical archives. All specimens are catalogued and retrieved utilizing the clinical laboratory information systems, in accordance with CAP/JCAHO regulations. The use of any stored specimens for research purposes is only allowed when the appropriate IRB approval has been obtained. In some cases, this approval has been obtained via the original protocol on which the patient was enrolled.

5.2.3 Thoracic Epigenetics Laboratory

This study will be conducted within the Thoracic Surgery Branch, NCI. Sample collection and initial processing will be performed in the Thoracic Epigenetics Laboratory (TEL). Samples will be stored in designated monitored freezers (at least -20°C). All samples obtained on this study will be tracked using Labmatrix. Pharmacokinetic samples will be analyzed in the [name] Lab, GMB. Samples will be identified and tracked using unique identifiers linked to each subject's unique patient number (study number). Codes linking personal identifiable information to the unique identifier will be stored in secure, computer servers with limited coded access or locked file cabinets in the Thoracic Surgery Branch, with access limited to the PI or study coordinator. Gene expression, microRNA, and DNA methylation signatures, as well as methylation status of circulating tumor DNA and serologic responses to treatment will be analyzed in [name] laboratory.

5.2.5 Sample Destruction, End of Protocol Procedures

All specimens obtained in the protocol are used as defined in the protocol. Any specimens that are remaining at the completion of the protocol will be stored in the conditions described below. The study will remain open so long as sample or data analysis continues.

Following completion of this study, if the subject has co-enrolled on 06C0014, samples will be transferred to the Tissue Procurement protocol and remain in storage in the Blood Processing Core (BPC) as detailed within 06C0014. Access to these samples will only be granted following IRB approval of an additional protocol, granting the rights to use the material. If the subject has not co-enrolled on the Tissue Procurement protocol, the samples will be destroyed.

If the patient withdraws consent the participants data will be excluded from future distributions, but data that have already been distributed for approved research use will not be able to be retrieved.

The PI will record any loss or unanticipated destruction of samples as a deviation. Reporting will be per the requirements of Section 7.2.

6 DATA COLLECTION AND EVALUATION

6.1 DATA COLLECTION

For the purposes of the research sample analyses and correlation with clinical outcomes, demographic information, histology, operative and peri-operative interventions, pathologic findings, laboratory and imaging parameters (performed as part of routine or protocol specified patient care) may be collected on this study. The PI will be responsible for overseeing entry of data into a 21 CFR Part 11-compliant data capture system provided by the NCI CCR and ensuring data accuracy, consistency and timeliness. The principal investigator, associate investigators/research nurses and/or a contracted data manager will assist with the data management efforts. Primary and final analyzed data will have identifiers so that research data can be attributed to an individual human subject participant.

End of Study Procedures: Data will be stored according to HHS, FDA regulations, and NIH Intramural Records Retention Schedule as applicable.

Loss or Destruction of Data: Should we become aware that a major breach in our plan to protect subject confidentiality and trial data has occurred, this will be reported expeditiously per requirements in Section 7.2.1.

6.1.1 Routine Data Collection

Following registration, all adverse events will be described in the source documents, reviewed by the designated research nurse, and captured.

All adverse events, including clinically significant abnormal findings on laboratory evaluations, regardless of severity, will be followed until return to baseline or stabilization of event. Document AEs from the first study intervention, Study Day 1, through 30 days after the last administration of study therapy. Beyond 30 days after the last intervention, only adverse events which are serious and related to the study intervention need to be recorded.

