3 STUDY IMPLEMENTATION

3.1 STUDY DESIGN

This trial is unique in that it is intended to establish the rationale and conditions for the use of oral DAC-THU and pembrolizumab therapy for NSCLC, EsC, and MPM. The goal is to establish the basis for subsequent evaluation of this treatment regimen in combination with other agents targeting MDSC, or adoptive immunotherapy regimens in patients with thoracic malignancies.

Patients potentially eligible for trial will be evaluated, and undergo subsequent eligibility assessment in the Thoracic Surgery Clinic/NCI. Patients meeting eligibility criteria will undergo baseline (if fresh tumor biopsy was not performed at screening) and post treatment tumor biopsies either by percutaneous image-guided FNA techniques in Interventional Radiology (Clinical Center/NIH) or endoscopic/thoracoscopic techniques in the CC operating room by Thoracic Surgery staff using standard of care practice guidelines. Tumor biopsies may be omitted at the discretion of the PI if risks outweigh potential research benefits.

The Phase I component will be a standard 3+3 design starting with oral DAC-THU on two consecutive days (preferably Tuesday and Wednesday) for two weeks out of three weeks for 9

weeks with incremental dose escalation as shown in Section **3.1.3**. Patients with high PD-L1 tumor expression will be combined with patients with low PD-L1 tumor expression to minimize accrual numbers required for the Phase I component of the study. Pembrolizumab will be administered on Wednesday, Thursday or Friday at a fixed intravenous dose of 200 mg q 3 weeks. One cycle is three weeks; one course is 9 weeks. Treatment evaluation including repeat tumor biopsy will be performed after one course of therapy (Week 10 +/- one week). Those patients exhibiting disease progression or unacceptable toxicities will be removed from study. Patients exhibiting stable disease or disease regression will be offered an additional course of therapy followed by treatment evaluation (without mandatory biopsy). Treatment will continue in this manner until off-study criteria have been met.

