6.3.2 Definitions

Evaluable for toxicity: All patients will be evaluable for toxicity from the time of their first treatment with DAC/THU/pembrolizumab. Dose limiting toxicities will be assessed during the first 3 weeks of DAC-THU/pembrolizumab therapy.

Evaluable for objective response: Patients who have measurable disease present at baseline, have received at least 9 weeks of DAC-THU/pembrolizumab therapy (one full course), and have had their disease re-evaluated will be considered evaluable for response provided: (1) the patient demonstrates progressive disease or death while on protocol therapy; (2) the tumor is not removed surgically prior to the time complete response or partial response is confirmed; or (3) the patient demonstrates a complete or partial response as confirmed according to protocol criteria. These patients will have their response classified according to the definitions stated below. [Note: Patients who electively terminate therapy before completing 9 weeks of DAC-THU/pembrolizumab therapy and do not expire within 14 days from start of treatment will be replaced. Patients who experience disease progression after 3 weeks of drug therapy but before

completing the minimum of 9 weeks of drug therapy will be taken off-treatment and will only be evaluable for toxicity (not evaluable for response)].

Evaluable Non-Target Disease Response: Patients who have lesions present at baseline that are evaluable but do not meet the definitions of measurable disease, have received at least 8 weeks of DAC-THU/pembrolizumab therapy, and have had their disease re-evaluated will be considered evaluable for non-target disease. The response assessment is based on the presence, absence, or unequivocal progression of the lesions.

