8.2 ASSESSMENT OF SAFETY EVENTS

AE information collected will include event description, date of onset, assessment of severity and relationship to study product and alternate etiology (if not related to study product), date of resolution of the event, seriousness and outcome. The assessment of severity and relationship to the study product will be done only by those with the training and authority to make a diagnosis and listed on the Form FDA 1572 as the site principal investigator or sub-investigator. AEs occurring during the collection and reporting period will be documented appropriately regardless of relationship. AEs will be followed through resolution.

SAEs will be:

- Assessed for severity and relationship to study product and alternate etiology (if not related to study product) by a licensed study physician listed on the Form FDA 1572 as the site principal investigator or sub-investigator.
- Recorded on the appropriate SAE report form, the medical record and captured in the clinical database.

• Followed through resolution by a licensed study physician listed on the Form FDA 1572 as the site principal investigator or sub-investigator.

For timeframe of recording adverse events, please refer to Section 6.1. All serious adverse events recorded from the time of first investigational product administration must be reported to the Sponsor with the exception of any listed in Section 8.4.

8.3 **Reporting of Serious Adverse Events**

Any AE that meets protocol-defined serious criteria or meets the definition of Adverse Event of Special Interest that require expedited reporting must be submitted immediately (within 24 hours of awareness) to OSRO Safety using the CCR SAE report form. Any exceptions to the expedited reporting requirements are found in Section **8.4**.

All SAE reporting must include the elements described in Section 8.2.

SAE reports will be submitted to the Center for Cancer Research (CCR) at: [contact] and to the CCR PI and study coordinator. CCR SAE report form and instructions can be found at: https://ccrod.cancer.gov/confluence/display/CCRCRO/Forms+and+Instructions

Following the assessment of the SAE by OSRO, other supporting documentation of the event may be requested by the OSRO Safety and should be provided as soon as possible.

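### Adverse event start points conflict, so a serious complication of a pre-dose baseline research biopsy is not assured a place in the safety data or in sponsor SAE reports

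*Combined protocol and SAP*

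**What the plan says.** **When safety capture starts.**
- Section 6.1.1, first paragraph: "Following registration, all adverse events will be described in the source documents, reviewed by the designated research nurse, and captured".
- Section 6.1.1, second paragraph: "Document AEs from the first study intervention, Study Day 1, through 30 days after the last administration of study therapy".
- Section 6.3.2: "All patients will be evaluable for toxicity from the time of their first treatment with DAC/THU/pembrolizumab".
- Section 8.2: "All serious adverse events recorded from the time of first investigational product administration must be reported to the Sponsor". For the recording period, this section refers back to Section 6.1.
- Appendix 3: as the table can be read, the adverse event row begins at Day 1 of DAC-THU, while the research tumor sample and concomitant medications have entries in the baseline column.

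**When the biopsies are done.**
- Section 3.4.1 places the baseline biopsy under "Any Time Prior to Initiation of Treatment", on the condition "Tumor biopsy if fresh sample from previous biopsy is not available". It adds: "Samples collected on 06C0014 or any other NCI protocol in which the patient is co-enrolled can be used".
- Section 3.1 has eligible patients biopsied at baseline and after treatment, by "percutaneous image-guided FNA techniques in Interventional Radiology" or by endoscopic or thoracoscopic technique in the operating room. The PI may omit a biopsy when its risks outweigh the research benefit.
- Section 3.1.1 and Appendix 3 (footnote 8) put the second biopsy after one course, around week 10.
- Section 11.4.1.8 counts two CT-guided biopsies in the radiation exposure that it describes as purely for research.

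**The concern.** The baseline biopsy is an invasive procedure that this protocol may perform for research. It comes before the point at which three of the four safety rules, and apparently the calendar, begin. The fourth rule, the registration sentence in 6.1.1, points the other way and is contradicted in the next paragraph of the same section.

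A site that follows the Day 1 sentence and Section 8.2 as written could treat a bleed or a pneumothorax needing admission after the baseline biopsy as outside both the adverse event record and the sponsor SAE stream. The same event after the week 10 biopsy would be recorded and reported. What is at stake is complete reporting of serious harm from a research procedure. No efficacy estimate depends on it.

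**Working it through.** The plan states no figure on this point, so the check sets the texts side by side, with some day arithmetic from the calendar in Section 3.1.

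**1. Where the baseline biopsy falls.** Section 3.4.1 puts it before treatment starts, and Section 3.1 puts it after eligibility is met. Against each rule, a complication before first dose is:
- 6.1.1, registration sentence: inside, if the biopsy follows registration.
- 6.1.1, Study Day 1 sentence: outside.
- 6.3.2, toxicity evaluability: outside.
- 8.2, sponsor SAE reporting: outside.
- Appendix 3, adverse event row: apparently outside.

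**2. Where the second biopsy falls.** Inputs: the calendar numbers Sunday of Week 1 as Day 0, which makes Wednesday of Week 8 Day 52 and Wednesday to Friday of Week 7 Days 45 to 47. Table 7 gives DAC-THU in weeks 1, 2, 4, 5, 7 and 8. Pembrolizumab every three weeks puts its third Course 1 dose in Week 7. Section 3.1.1 sets the biopsy at Days 64 and 65, plus or minus 7 days.
- Biopsy range: 64 − 7 = Day 57 to 65 + 7 = Day 72.
- Adverse event window from the last DAC-THU dose: 52 + 30 = Day 82.
- Window counted from the last pembrolizumab dose alone: 45 + 30 = Day 75 to 47 + 30 = Day 77.

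Day 72 is before Day 75, so the second biopsy is inside the window on either count if Course 1 runs to schedule.

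**3. Which events differ between the two biopsies.** Section 6.1.2.1 keeps all Grade 1 events, and Grade 2 events unrelated to treatment, in source documents only, whenever they occur. Low-grade biopsy complications of that kind would go unrecorded at both time points. The difference is confined mainly to Grade 3 or higher or serious events.

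**4. How many patients.**
- Lower bound 0: every patient could have a fresh sample already, have tissue from another NCI protocol, or have the biopsy omitted.
- Upper bound 85: the accrual ceiling in Section 10, which also says the trial may finish with 60 or fewer.
- The range is real. Section 2.2 accepts archival tissue for histology, so a patient confirmed on archival tissue alone may have no fresh sample and then meets the condition for a baseline biopsy.

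The documents give no complication rate. Assuming 2% to 10% for complications of any grade, purely as illustration:
- 85 biopsies: 85 × 0.02 = 1.7 to 85 × 0.10 = 8.5.
- 42 biopsies (about half): 42 × 0.02 = 0.8 to 42 × 0.10 = 4.2.
- 0 biopsies: 0.

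Grade 3 or higher or serious events would be a subset of these.

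**The case against.** The strongest reply is that 6.1.1 already captures adverse events from registration, so a biopsy done under this protocol is covered. This stands in part. It rules out the inference that a patient harmed by the baseline biopsy who never starts drug would appear nowhere: source documentation applies from registration. It does not close the gap, because the Day 1 sentence contradicts it and Section 8.2 still ties mandatory sponsor reporting to first administration.

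The phrase about a first study intervention could be read to include a biopsy. The text equates it with Study Day 1, and 6.3.2 and 8.2 point to first dose.

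Other routes exist. Section 7.2.1 refers research events to NIH policies that cannot be examined here, and Section 7.3 requires notice of deaths within 30 days of a research intervention unless due to progression. Section 8.3 asks for SAE reports without naming a start date. The first two stand, but neither puts a non-fatal admission into the toxicity tables of Section 10.1 or the sponsor stream. Section 8.3 does not settle the matter, because 8.2 sets the start and 8.1.1 defines an adverse event in a subject given a pharmaceutical product.

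Finally, starting drug-safety collection at first dose is a coherent choice, and no objective compares the two biopsies. Both points stand. The request is to assure reporting of procedural harm, leaving the drug-toxicity window as it is.

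**Conclusion.** The point holds as an internal conflict with a practical gap. A Grade 3 or higher or serious complication of a baseline research biopsy, done under this protocol after registration and before first dose, is not assured a place in the safety data or in mandatory sponsor SAE reports. The same event after the week 10 biopsy is inside the window.

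The size is unknown: 0 to 85 patients could have the procedure. A reader might infer that about 2 to 8 events would be lost. The documents do not support this. It would require all 85 patients to be biopsied under this protocol, a complication rate taken from no source here, and a count that includes low-grade events which Section 6.1.2.1 leaves unrecorded at any time. A reader might also infer that research biopsies as a whole escape safety capture; only the baseline one is affected.

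The conclusion assumes that Study Day 1 means the start of treatment, that Course 1 runs to schedule, and that the Appendix 3 row has been read correctly from a broken table. The response analyses and the DLT rule do not change. The amendment is worth making because it is cheap and concerns participant safety.

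**What to change.** Reconcile Sections 6.1.1, 6.3.2, 8.2 and Appendix 3:
- In 6.1.1, replace the two start points with one rule: procedure-related adverse events are recorded from the first research procedure performed under this protocol after registration, and all other adverse events from first dose.
- In 8.2, require procedure-related SAEs to be reported to the sponsor from that same point, whether or not the patient later receives study drug, and say so despite the definition in 8.1.1.
- In 6.3.2, keep first dose as the start for drug toxicity and DLT, and have procedure-related events tabulated separately.
- In Appendix 3, add a baseline entry to the adverse event row for procedure-related events.
- In 6.1.2.1, state whether the exclusion of treatment-unrelated Grade 2 events applies to procedure-related events.

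The cost is a few sentences of amendment, a few extra data entries and possibly some SAE reports. No visit, test or procedure is added.
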